#### **3.6.1 Treatment Discontinuation**

Subjects will receive study treatment until treatment discontinuation for any of the reasons listed below. Subjects may discontinue study treatment and assessments or withdraw their consent to participate in the study at any time without prejudice. If a subject discontinues all study treatment, the reason will be documented in source documents and all study treatment will be stopped. The investigator may also discontinue a subject from all study treatment if in his or her clinical judgment it is in the best interest of the subject or if the subject cannot comply with the protocol. In addition, the Investigator will also discontinue a subject from study treatment upon the Sponsor's request or if the Sponsor chooses to terminate the study.

The following are possible reasons for discontinuation of all study treatment:

- Subject no longer experiences clinical benefit as determined by the Investigator (eg, disease progression [PD] and/or clinical deterioration attributable to PD where either is unlikely to reverse with continued study treatment and/or supportive care).
- Unacceptable side effects the Investigator feels may be due to study treatment. Continuation of one component of the combination study treatment while discontinuing the other will be allowed. The Investigator is encouraged to discuss such circumstances with the Sponsor.
- The investigator feels it is not in the best interest of the subject to continue on study.

CONFIDENTIAL

Protocol XL184-313 Protocol Amendment 3.0  
Page 53 of 193

- Subject participation in another clinical study using an investigational agent, investigational medical device, or other intervention.
- Necessity for treatment with non-protocol systemic anti-cancer therapy.
- Necessity for interrupting all study treatment for greater than 12 weeks for study-treatment related AEs unless approved by the Sponsor. (Note: temporary interruptions of study treatment for greater than 12 weeks due to the effects of COVID-19 and unrelated to AEs are described in [Appendix K](#).)
- Refusal of sexually active fertile subjects to use highly effective methods of contraception (defined in [Appendix D](#)).
- Female subjects who become pregnant.
- Request by the Sponsor
- Unblinding of study treatment by the Investigator (prior to unblinding of study treatment for all subjects)
- Subject request to discontinue all study treatments (with or without concurrent withdrawal of informed consent).

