- g. Serum creatinine  $\leq 1.5 \times$  ULN or calculated creatinine clearance  $\geq 40$  mL/min ( $\geq 0.67$  mL/sec) using the Cockcroft-Gault equation (see [Table 5-3](#) for Cockcroft-Gault formula).
- h. Urine protein-to-creatinine ratio (UPCR)  $\leq 1$  mg/mg ( $\leq 113.2$  mg/mmol), or 24-h urine protein  $\leq 1$  g.

9. Capable of understanding and complying with the protocol requirements and must have signed the informed consent document prior to any screening assessments except those procedures performed as standard of care within the screening window.

10. Sexually active fertile subjects and their partners must agree to use highly effective methods of contraception (defined in [Appendix D](#)) during the course of the study and for 5 months for women, and 7 months for men, after the last dose of study treatment. A barrier contraceptive method (eg, condom) is also required.

11. Female subjects of childbearing potential must not be pregnant at screening. Female subjects are considered to be of childbearing potential unless one of the following criteria are met: documented permanent sterilization (hysterectomy, bilateral salpingectomy, or bilateral oophorectomy) or documented postmenopausal status (defined as 12 months of amenorrhea in a woman  $> 45$  years-of-age in the absence of other biological or physiological causes. In addition, females  $< 55$  years-of-age must have a serum follicle stimulating hormone (FSH) level  $> 40$  mIU/mL to confirm menopause). Note: Documentation may include review of medical records, medical examination, or medical history interview by study site staff.

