## **Appendix D: Highly Effective Methods of Contraception**

In Inclusion Criterion #10 (Section 4.2), sexually active fertile subjects and their partners must agree to use highly effective methods of contraception that alone or in combination result in a failure rate of less than 1% per year when used consistently and correctly during the course of the study and until the end of relevant systemic exposure, defined as 5 months for women, and 7 months for men, after the last dose of study treatment.

The effect of cabozantinib on the PK of contraceptive steroids has not been investigated. Because oral contraceptives might possibly not be considered as “effective methods of contraception,” they should be used together with another method.

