### Highly effective contraceptive methods that are user independent:

- Implantable progestogen-only hormonal contraception associated with inhibition of ovulation

CONFIDENTIAL

Protocol XL184-313 Protocol Amendment 3.0  
Page 160 of 193

- Hormonal methods of contraception including oral contraceptive pills containing a combination of estrogen and progesterone, vaginal ring, injectables, implants and intrauterine hormone-releasing system
- Intrauterine device
- Bilateral tubal occlusion
- Vasectomized partner
  - A vasectomized partner is a highly effective contraception method provided that the partner is the sole male sexual partner of the female subject of childbearing potential and the absence of sperm has been confirmed. If not, an additional highly effective method of contraception should be used
- Sexual abstinence
  - Sexual abstinence is considered a highly effective method only if defined as refraining from heterosexual intercourse during the entire period of risk associated with the study drug. The reliability of sexual abstinence needs to be evaluated in relation to the duration of the study and the preferred and usual lifestyle of the participant.
    - It is not necessary to use any other method of contraception when complete abstinence is elected.
    - Female subjects of childbearing potential who choose complete abstinence must continue to have pregnancy tests per the protocol. Acceptable alternate methods of highly effective contraception must be discussed in the event that any of these subjects chooses to forego complete abstinence.

CONFIDENTIAL

Protocol XL184-313 Protocol Amendment 3.0  
Page 161 of 193

Acceptable barrier methods for use in combination with a highly effective method:

- Male or female condom with or without spermicide
- Diaphragm with spermicide
- Cervical cap with spermicide
- Vaginal Sponge with spermicide

Unacceptable as a Sole Method of Contraception:

- Male or female condom with or without spermicide. Male and female condoms cannot be used simultaneously
- Diaphragm with spermicide
- Cervical cap with spermicide
- Vaginal Sponge with spermicide
- Progestogen-only oral hormonal contraception of which inhibition of ovulation is not the primary mechanism of action
- Periodic abstinence (eg, calendar, symptothermal, post-ovulation methods)
- Withdrawal (eg, coitus interruptus).
- Spermicide only
- Lactation amenorrhea method

CONFIDENTIAL

Protocol XL184-313 Protocol Amendment 3.0  
Page 162 of 193

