## **Contraception guidance for male participants with partner(s) of childbearing potential**

Male subjects with female partners of childbearing potential are eligible if they agree to the following during the treatment and until the end of relevant systemic exposure, defined as 7 months after the last dose of study treatment.

- Inform any and all partner(s) of their participation in a clinical drug study and the need to comply with contraception instructions as directed by the Investigator.
- Male subjects are required to use a condom during study duration and until end of relevant systemic exposure, defined as 7 months after the last dose of study treatment.
- Female partners of male subjects in the study to consider use of effective methods of contraception until the end of relevant systemic exposure, defined as 7 months after the last dose of treatment in the male participant.

Male subjects with a pregnant or breastfeeding partner must agree to remain abstinent from penile-vaginal intercourse or use a male condom during each episode of penile penetration during the treatment and until 7 months after the last dose of study treatment. Refrain from donating sperm for the duration of the study treatment and until 7 months after the last dose of study treatment.

CONFIDENTIAL

Protocol XL184-313 Protocol Amendment 3.0  
Page 163 of 193

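### Criterion 10 binds male subjects and their partners to highly effective contraception, but the male section of Appendix D admits men on condom use while the partner need only consider an effective method

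*Protocol*

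**What the plan says.** Criterion 10 appears in the synopsis and in Section 4.2 with the same wording: "Sexually active fertile subjects and their partners must agree to use highly effective methods of contraception". It refers to Appendix D for the definition, sets the period at 5 months (women) and 7 months (men) after the last dose, and adds "A barrier contraceptive method (eg, condom) is also required".

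Appendix D opens by citing criterion 10 and restating the duty for subjects and partners, with methods "that alone or in combination result in a failure rate of less than 1% per year when used consistently and correctly". Section 8.5.1 says that highly effective methods must continue for the same periods, so it covers men for 7 months.

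The male section of Appendix D has its own eligibility sentence: "Male subjects with female partners of childbearing potential are eligible if they agree to the following during the treatment". The items under it are to inform partners, to use a condom, and "Female partners of male subjects in the study to consider use of effective methods of contraception". Further lines cover pregnant or breastfeeding partners and sperm donation and do not bear on this point.

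Section 3.6.1 includes, among possible reasons for stopping all study treatment, "Refusal of sexually active fertile subjects to use highly effective methods of contraception", again with a pointer to Appendix D. Section 4.1 says that the sponsor will not waive eligibility criteria.

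**The concern.** Two sets of passages govern the entry of the same men and do not agree. One makes the partner's agreement to a highly effective method a condition of entry. The other makes the man eligible on his own undertakings and leaves her a recommendation of a weaker class.

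The study plans about 180 sites (Section 3.1). A site that works from criterion 10 and one that works from the male section could reach opposite decisions on the same man, and could give partners different instructions about avoiding pregnancy. The duty lasts through treatment and 7 months beyond, so the question does not end at screening. Section 8.5.1 also makes a partner's pregnancy reportable, with follow-up.

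**Working it through.** No arithmetic applies, and the plan gives no figure to reproduce. The check sets the passages side by side.

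| Place in the protocol | Who is bound | Method | Force |
|---|---|---|---|
| Criterion 10 (synopsis; Section 4.2) | Subject and partner | Highly effective, plus a barrier | Mandatory for entry |
| Appendix D, opening | Subject and partner | Highly effective, failure below 1% per year | Mandatory for entry |
| Section 8.5.1 | Subjects, men included | Highly effective | Mandatory to continue |
| Appendix D, male section | The man | Inform partners; condom | Condition of eligibility |
| Appendix D, male section | The partner | Effective | To consider |

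1. **Duration.** All these places give 7 months for men. There is no conflict here.
2. **Force.** Criterion 10 and the Appendix D opening require the partner to agree. The male section asks her to consider. These differ.
3. **Method class.** Highly effective in the first three rows, effective in the last. These differ.
4. **Can the condom itself be the highly effective method?** Criterion 10 asks for a barrier in addition and gives the condom as its example of one. A condom therefore meets the additional element and leaves the main one unmet. The male section never describes its own measures as highly effective.
5. **Test case A.** A fertile, sexually active man informs his partner and agrees to use condoms. She considers other methods and adopts none.
   - Male section: every item is met, so he is eligible.
   - Criterion 10 and the Appendix D opening: the partner has not agreed to a highly effective method, so he is not eligible.
6. **Test case B.** The same man, but his partner agrees to a highly effective method. He passes both tests. The conflict is thus confined to couples in which the partner does not take up such a method.
7. **Can a site settle it locally?** Section 4.1 excludes waivers, so case A cannot be resolved by exception.

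**The case against.** The best defence is that criterion 10 defers to Appendix D, that Appendix D gives guidance by sex, and that the specific male text governs the general statement. A site could reasonably follow that route. But the cross-reference leads to both rules, because Appendix D opens by restating the strict duty for subjects and partners before it reaches the male section, and Section 8.5.1 applies the highly effective standard to men again.

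A second defence reads the male items as additions to the general rule. That leaves the partner line with no function: someone already bound to a highly effective method has no need to consider an effective one.

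Several further points against a larger claim do stand:

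- A reader might infer that the man in test case A already meets a reason to stop treatment. Section 3.6.1 lists possible reasons only and concerns refusal by subjects, not partners. He has refused nothing. The section belongs in the reconciliation only because it relies on Appendix D.
- A reader might cite the list headed "Unacceptable as a Sole Method of Contraception", which includes the male condom. It falls under the guidance for female subjects and does not govern men. Step 4 of the check does not use it.
- Divergent practice between sites is a possibility. Nothing in the documents shows that it has occurred.
- SAP Section 9 reports important deviations as pre-specified in a deviation management plan that is not among the documents. Whether a mismatch of this kind would count is unknown.

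**Conclusion.** The contradiction is real and stands in the current text. It concerns whether the partner's duty is mandatory or advisory, which class of method applies, and whether a condom alone is enough. It does not concern duration.

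Its reach is limited to fertile, sexually active male subjects whose partner of childbearing potential does not adopt a highly effective method. A reader might want a headcount. The documents do not support one: they give no split by sex, age or partner status, and a count of men who have such partners would exceed the number caught by the conflict. Nor can all 840 planned subjects serve as the base. SAP Section 4.8.1 reports more than 17 months of minimum follow-up in the first 440 as of January 2022, which puts their randomization at about August 2020 or before. SAP Table 1 dates Amendment 3.0 to 16 November 2020, and the wording of criterion 10 in earlier protocol versions cannot be seen here.

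No endpoint, estimand, analysis population, power, alpha or event count is affected. The consequence is for eligibility decisions, the classification of deviations, and the instructions given to partners. The conclusion rests on a comparison of wording alone and on no assumed figure.

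**What to change.** State one requirement for male subjects and their partners, in the same terms, in five places: criterion 10 in the synopsis, criterion 10 in Section 4.2, Section 8.5.1, the opening of Appendix D, and the male section of Appendix D. It should settle three things:

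- whether the partner's undertaking is a condition of eligibility or advice;
- which class of method applies to the man and to his partner;
- whether condom use alone is sufficient for a male subject.

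Then align the cross-reference in Section 3.6.1, so that the discontinuation item points to the same standard for men. The sponsor decides which standard applies; this review takes no position on it.

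The cost is wording only, at the next amendment, with a memo to sites in the meantime and a check that the consent form matches. No analysis or data collection changes.

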#### 4.3 Exclusion Criteria

- 1. Prior systemic anticancer therapy for unresectable locally advanced or metastatic RCC including investigational agents.
 

*Note: One prior systemic adjuvant therapy is allowed for completely resected RCC and if recurrence occurred at least 6 months after the last dose of adjuvant therapy.*

*Note: Adjuvant therapy with a PD-1 or PD-L1 inhibitor in combination with a CTLA-4 inhibitor is not permitted.*
- 2. Radiation therapy for bone metastasis within 2 weeks, any other radiation therapy within 4 weeks prior to randomization. Subjects with clinically relevant ongoing complications from prior radiation therapy are not eligible.
- 3. Known brain metastases or cranial epidural disease unless adequately treated with radiotherapy and/or radiosurgery and stable for at least 4 weeks prior to

CONFIDENTIAL

Protocol XL184-313 Protocol Amendment 3.0  
Page 57 of 193

randomization after radiotherapy or at least 4 weeks prior to randomization after major surgery (eg, removal or biopsy of brain metastasis). Subjects who are neurologically symptomatic as a result of their CNS disease, or are receiving systemic corticosteroid treatment (prednisone equivalent > 10 mg/day) at the planned time of randomization are not eligible.

4. Concomitant anticoagulation with oral anticoagulants (eg, warfarin, direct thrombin and Factor Xa inhibitors) or platelet inhibitors (eg, clopidogrel).

a. Allowed anticoagulants are:

- i. Low-dose aspirin for cardioprotection (per local applicable guidelines) and low-dose low molecular weight heparins (LMWH)
- ii. Therapeutic doses of LMWH in subjects without known brain metastases who are on a stable dose of LMWH for at least 1 week before randomization without clinically significant hemorrhagic complications from the anticoagulation regimen or the tumor

*Note: Subjects who switch from an oral anticoagulant to LMWH are allowed if the oral anticoagulant was stopped  $\geq$  5 half-lives of the oral anticoagulant prior to planned randomization date.*

5. Administration of a live, attenuated vaccine within 30 days prior to randomization. The use of inactivated (killed) vaccines for the prevention of infectious disease is permitted.

6. The subject has uncontrolled, significant intercurrent or recent illness including, but not limited to, the following conditions:

a. Cardiovascular disorders:

- i. Congestive heart failure (CHF) class III or IV as defined by the New York Heart Association, unstable angina pectoris, serious cardiac arrhythmias (eg, ventricular flutter, ventricular fibrillation, Torsades de pointes).
- ii. Uncontrolled hypertension defined as sustained blood pressure (BP)  $> 150$  mm Hg systolic or  $> 90$  mm Hg diastolic despite optimal antihypertensive treatment.
- iii. Stroke, transient ischemic attack (TIA), myocardial infarction, or other symptomatic ischemic event or thromboembolic event (eg, deep venous thrombosis, pulmonary embolism [DVT/PE]) within 6 months before randomization.

*Note: Subjects with a diagnosis of DVT within 6 months are allowed if asymptomatic and stable at screening and treated with LMWH for at least 1 week before randomization.*

*Note: Non-symptomatic white matter disease in the brain is acceptable.*

b. Gastrointestinal (GI) disorders including those associated with a high risk of perforation or fistula formation:

CONFIDENTIAL

Protocol XL184-313 Protocol Amendment 3.0  
Page 58 of 193

- i. Tumors invading the GI-tract, active peptic ulcer disease, inflammatory bowel disease, diverticulitis, cholecystitis, symptomatic cholangitis or appendicitis, acute pancreatitis or acute obstruction of the pancreatic or biliary duct, or gastric outlet obstruction.
- ii. Abdominal fistula, GI perforation, bowel obstruction, or intra-abdominal abscess within 6 months prior to randomization. Complete healing of an intra-abdominal abscess must be confirmed prior to randomization.
- c. Clinically significant hematuria, hematemesis, or hemoptysis of > 0.5 teaspoon (2.5 mL) of red blood, or other history of significant bleeding (eg, pulmonary hemorrhage) within 3 months before randomization.
- d. Cavitating pulmonary lesion(s) or known endobronchial disease manifestation.
- e. Lesions invading major pulmonary blood vessels.
- f. Other clinically significant disorders such as:
  - i. Autoimmune disease that has been symptomatic or required treatment within the past two years from the date of randomization.
 

*Note: Patients with a history of Crohn's disease or ulcerative colitis are always excluded*

*Note: Subjects with type I diabetes mellitus, hypothyroidism only requiring hormone replacement, skin disorders (such as vitiligo, psoriasis, or alopecia) not requiring systemic treatment, or conditions not expected to recur in the absence of an external trigger are permitted to enroll.*
  - ii. Any condition requiring systemic treatment with either corticosteroids (> 10 mg daily prednisone equivalent) or other immunosuppressive medications within 14 days of randomization.
 

*Note: Inhaled, intranasal, intra-articular, or topical steroids are permitted. Adrenal replacement steroid doses > 10 mg daily prednisone equivalent are permitted. Transient short-term use of systemic corticosteroids for allergic conditions (eg, contrast allergy) is also allowed.*
  - iii. Active infection requiring systemic treatment. Acute or chronic hepatitis B or C infection, known human immunodeficiency virus (HIV) or acquired immunodeficiency syndrome (AIDS)-related illness, or known positive test for tuberculosis infection where there is clinical or radiographic evidence of active mycobacterial infection.
  - iv. History of idiopathic pulmonary fibrosis, organizing pneumonia, drug-induced pneumonitis, idiopathic pneumonitis, or evidence of active pneumonitis on screening chest computed tomograph (CT) scan
  - v. Serious non-healing wound/ulcer/bone fracture.
  - vi. Malabsorption syndrome.
  - vii. Uncompensated/symptomatic hypothyroidism.

CONFIDENTIAL

Protocol XL184-313 Protocol Amendment 3.0  
Page 59 of 193

- viii. Moderate to severe hepatic impairment (Child-Pugh B or C) ([Appendix J](#)).
- ix. Requirement for hemodialysis or peritoneal dialysis.
- x. History of solid organ or allogeneic stem cell transplant.
- xi. Known history of COVID-19 unless the subject has clinically recovered from the disease at least 30 days prior to randomization.

7. Major surgery (eg, nephrectomy, GI surgery, removal or biopsy of brain metastasis) within 4 weeks prior to randomization. Minor surgeries within 10 days prior to randomization. Subjects must have complete wound healing from major or minor surgery before randomization. Subjects with clinically relevant ongoing complications from prior surgery are not eligible.

8. Corrected QT interval calculated by the Fridericia formula (QTcF)  $> 500$  ms per electrocardiogram (ECG) within 14 days before randomization. Furthermore, subjects with a history of additional risk factors for torsades de pointes (eg, long QT syndrome) are also excluded.

*Note: If a single ECG shows a QTcF with an absolute value  $> 500$  ms, two additional ECGs at intervals of approximately 3 min must be performed within 30 min after the initial ECG, and the average of these three consecutive results for QTcF will be used to determine eligibility*

- 9. History of neuropsychiatric disorder likely to interfere with ability to comply with protocol requirements or give informed consent.
- 10. Pregnant or breastfeeding females.
- 11. Inability to swallow tablets or unwillingness or inability to receive IV administration.
- 12. Previously identified allergy or hypersensitivity to components of the study treatment formulations or history of severe infusion-related reactions to monoclonal antibodies. Subjects with rare hereditary problems of galactose intolerance, the Lapp lactase deficiency or glucose-galactose malabsorption are also excluded.
- 13. Any other active malignancy at time of randomization or diagnosis of another malignancy within 3 years prior to randomization that requires active treatment, except for locally curable cancers that have been apparently cured, such as basal or squamous cell skin cancer, superficial bladder cancer, or carcinoma in situ of the prostate, cervix, or breast.

CONFIDENTIAL

Protocol XL184-313 Protocol Amendment 3.0  
Page 60 of 193

